In individuals 18 years and older with persistent asthma who remain symptomatic despite low dose inhaled corticosteroid and are vitamin D insufficient (<30 ng/ml), the addition of vitamin D is superior to placebo in reducing treatment failures.

B. Secondary Research Hypotheses

- (1) In individuals 18 years and older with persistent asthma who remain symptomatic despite low dose inhaled corticosteroid (ICS) and are vitamin D insufficient, the addition of vitamin D (ICS+D) is superior to placebo in achieving improved lung function in subgroups of interest those who are overweight/obese and African-Americans.
- (2) In individuals 18 years and older with persistent asthma who remain symptomatic despite low dose inhaled corticosteroid (ICS) and are vitamin D insufficient and have reduced corticosteroid responsiveness (defined by lung function change after oral corticosteroids), the addition of vitamin D (ICS+D) will be superior to placebo in improving lung function measures.
- (3) In individuals 18 years and older with persistent asthma who remain symptomatic despite low dose inhaled corticosteroid (ICS) and are vitamin D insufficient, the addition of vitamin D (ICS+D) will result in less severe and less frequent colds than placebo.

C. Primary Outcome Measure

Treatment failure is a well-defined asthma outcome reflecting overall asthma control that has been used previously in multiple clinical trials (79, 80). In addition, the ATS and ERS Statement on standardizing endpoints for clinical asthma trials (81) defines moderate exacerbations as events that

- require additional treatment to prevent progression to severe exacerbation. This endpoint has clinical utility given that clinical practice guidelines advise that exacerbations should be recognized and treated before they become severe (81). Treatment failure as defined in the current proposal and prior trials (79, 80) is consistent with the ATS/ERS definition of a moderate exacerbation a deterioration
- 5 in symptoms and/or lung function with increased rescue bronchodilator use that lasts 2 days or more

6 (81).

Treatment failure status will be defined as the occurrence of one or more of the following:

At-home measurements:

 Pre-bronchodilator PEF ≤65% of baseline on any 2 of 3 consecutive scheduled measurements.

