 - (8) Vitamin D levels. Initial and post-randomization vitamin D levels will be compared to above asthma outcomes. The area under the curve (AUC) for vitamin D levels will be calculated for all individuals and compared to asthma control, quality of life and physiologic measures. In addition, an analysis will be performed restricted to those individuals who achieved sufficient vitamin D levels (>30 ng/ml) during the trial compared to those that did not.
 - (9) Corticosteroid responsiveness. Change in lung function in corticosteroid unresponsive and

- 1 responsive individuals will be evaluated. Corticosteroid-responsive airflow obstruction will be defined
- 2 as a ≥5% improvement in FEV₁ following systemic corticosteroids.
- 3 (10) Total inhaled corticosteroid dose. Cumulative inhaled corticosteroid received dose during all
- 4 study phases (phases I, IIa and IIb) will be calculated and compared to asthma control, quality of life
- 5 and physiologic measures.
- 6 (11) Colds. In all individuals experiencing a cold during the trial, the potential impact of vitamin D
- 7 on respiratory tract infections will be evaluated. The frequency and severity of colds, as reflected by
- 8 the peak Wisconsin Upper Respiratory Symptom Survey-21 (WURSS-21) score (86) during the cold,
- 9 will be compared between those in the vitamin D treatment group to those receiving placebo.
- Secondary analysis of the severity of the cold will evaluate the effect of the intervention on day 1 and
- 11 2 WURSS-21 scores.
- 12 (12) Airway inflammation. Response to vitamin D based on presence of airway inflammation (≥ 3%
- sputum eosinophils) at baseline (visit 3) and change over time in airway inflammation.
- 14 (13) Stress. Levels of perceived stress will be assessed using an adapted version of the Perceived
- 15 Stress Scale (PSS) (87) in all individuals.
- 16 (14) Sinonasal disease. Rhinitis and sinusitis symptoms will be assessed using a Sinonasal
- 17 Questionnaire (SNQ) (88) in all individuals.

IV. PROTOCOL OVERVIEW

A. Protocol design

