- 3 Vitamin D Intake Questionnaire. Participant dietary intake of vitamin D (and other vitamin
- 4 supplements) will be assessed at visits 3 and 10 using a modified food frequency questionnaire (95).
- 5 Assessment of the responses to these questionnaires will help account for dietary sources of vitamin
- 6 D in addition to the study intervention.
- 7 Sun Exposure Questionnaire (SEQ). We will collect UV exposure history using a modification of
- the UV exposure questionnaire that is used in the Nurses' Health Study (Appendix C) (96) at visits 3
- 9 and 10. Briefly, this questionnaire will inquire about UV exposure information such as average hours
- per dayspent outdoors in summer and winter, and sunscreen and tanning salon habits.
- 11 Asthma-specific Impairment. Impairment from asthma, in terms of productivity loss and activity
- impairment, will be assessed using an asthma-specific version of the Work Productivity and Activity
- 13 Impairment questionnaire (WPAI:Asthma) in all participants. The WPAI:Asthma has been previously
- validated in a severe difficult-to-treat asthma population in The Epidemiology and Natural History of
- 15 Asthma: Outcomes and Treatment Regimens (TENOR) study (85). WPAI:Asthma questionnaire will
- be measured at visits 2 and 10.

24

- 17 Cold Questionnaire. In all individuals experiencing a cold during the trial, the potential impact of
- vitamin D on respiratory tract infections will be evaluated. The frequency and severity of self-reported
- 19 colds, as reflected by the peak Wisconsin Upper Respiratory Symptom Survey-21 (WURSS-21) score
- 20 (86) during the cold, will be compared between those in the vitamin D treatment group to those
- 21 receiving placebo. Instructions on how to complete the WURSS-21 at the onset of cold symptoms will
- 22 be reviewed at visit 4 and reinforced at each subsequent visit. Secondary analysis of the severity of
- the cold will evaluate the effect of the intervention on day 1 and 2 WURSS-21 scores.
 - Stress Questionnaire (PSS). Psychological stress is a well known co-morbidity in asthma that

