The secondary hypothesis to evaluate the effect of supplementation with Vitamin D on the severity of colds will be addressed by fitting a RM-ANOVA model to the peak WURSS-21 cold scores during each cold, allowing for multiple colds within each participant. In addition to evaluating the average peak cold score from each cold, the average score on day 1 and day 2 will also be compared between

- the intervention and control groups. Additional models will be fit to the peak, day 1, and day 2 cold scores with adjustment for center and other important baseline covariates. Assuming that the incidence of colds is similar in our study to that seen in the ACRN PAX trial (125), a sample size of 200 per group could produce approximately 65 participants per group who experience at least one cold (32.4%). We will have at least the following power to detect the following effect sizes, assuming that the power in our analyses will be increased by the inclusion of multiple colds for each person.
- Power estimates assuming an overall alpha=0.05, 2-sided tests, and assuming a standard deviation = 32 from the ACRN PAX trial

Subset	Sample size	Power	Effect Size
Participants with self-	65 per group (32.4%)	80%	16
reported colds		85%	17
		90%	18

The cold scores at Day 1 and Day 2 will also be analyzed, and had similar estimates of standard deviation in the PAX trial.

Vitamin D dose analysis: a secondary analysis will be performed to evaluate the effect of received Vitamin D dose on the primary and secondary outcomes. To determine the potential effect of Vitamin D dose on the time to treatment failure, the received dose will be evaluated in a Cox regression model in two different ways: (1) as a time-varying covariate, and (2) as an average actual Vitamin D dose taken throughout the trial. To determine the potential effect of Vitamin D dose on the secondary outcomes, the received dose will be evaluated in a RM-ANOVA model for each outcome.

C. Missing data

Because of the possibility of drop-outs and other missed visits, there will be some missing data. The statistical models and analyses that are planned for the primary and secondary outcomes assume that the data are missing-at-random (MAR). Because likelihood-based methods will be applied, MAR data still yield valid estimates. Although not expected, if it appears that the MAR assumption is not reasonable, then nonignorable statistical analyses, such as pattern-mixture modeling, will be applied.

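### Hypothesis 3 covers both severity and frequency of colds, but Protocol VIII.B models and powers only severity, in a group formed after randomization by having had a cold

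*Protocol*

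**What the plan says.** Protocol III.B, hypothesis (3), has two parts: "the addition of vitamin D (ICS+D) will result in less severe and less frequent colds than placebo".

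The outcome definition in III.D(11) begins "In all individuals experiencing a cold during the trial, the potential impact of vitamin D" and continues "on respiratory tract infections will be evaluated. The frequency and severity of colds, as reflected by" the peak WURSS-21 score; these "will be compared between those in the vitamin D treatment group to those receiving placebo". VI.D (Cold Questionnaire) repeats the commitment: "vitamin D on respiratory tract infections will be evaluated. The frequency and severity of self-reported" colds are to be compared between arms.

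VIII.B then describes the hypothesis as one about severity. The method is "fitting a RM-ANOVA model to the peak WURSS-21 cold scores during each cold, allowing for multiple colds within each participant", with further models for the day 1 and day 2 scores and for covariate adjustment. The power table takes a cold incidence of 32.4% from an earlier network trial, hence about 65 people per group with a cold, and an SD of 32. It gives 80%, 85% and 90% power for differences of 16, 17 and 18 points. VIII.B names no model and gives no power for frequency.

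**The concern.** There are two linked problems.

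First, the document disagrees with itself. Three sections treat frequency as part of the question. The analysis section fixes the severity half in detail and leaves the frequency half out. The general method that VIII.B gives for secondary outcomes, a repeated-measures model of change from visit 3, does not fit a count of colds, which has no baseline value.

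Second, the severity comparison conditions on a post-randomization event. If vitamin D prevents some colds, the people with a cold in the vitamin D arm are no longer the counterparts of those in the placebo arm. A difference in mean peak score then mixes any effect on severity with the effect of which colds were prevented. The missing-at-random argument in VIII.C does not repair this: for someone without a cold the score is undefined, not missing.

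At stake is the interpretation of hypothesis 3. A real benefit could be masked, exaggerated or, under strong selection, given the wrong sign.

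**Working it through.** **Inputs from Protocol VIII.B:** 200 per group, cold incidence 32.4%, SD 32, two-sided alpha 0.05. Allocation is 1:1 (VI.A).

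**1. The plan's own table.** 200 × 0.324 = 64.8, so 65 per group. Detectable difference = (1.96 + z_power) × 32 × √(2/65), where 32 × √(2/65) = 5.613:

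- 80%: 2.802 × 5.613 = 15.7
- 85%: 2.996 × 5.613 = 16.8
- 90%: 3.242 × 5.613 = 18.2

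Power at 16, 17 and 18 points is 81.3%, 85.7% and 89.4%. The table reproduces and contains no arithmetic error.

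**2. What the table assumes about frequency.** It puts 65 people with colds in both arms, that is, no effect on frequency. Keep 65 on placebo and reduce the vitamin D number. Power for 16 points is then Φ(16 / [32 × √(1/65 + 1/n₂)] − 1.96):

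| Reduction in number with colds | n₂ | Power for 16 points |
|---|---|---|
| 0% | 65 | 81% |
| 20% | 52 | 77% |
| 30% | 46 | 74% |
| 40% | 39 | 69% |

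This loss is modest and involves no selection.

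**3. Size of the selection effect.** The documents give only the SD and the incidence, so the rest is assumed: normal peak scores, one cold per affected person, and no effect of vitamin D on the severity of the colds that still occur. Shift means the rise in mean score among the remaining vitamin D colds.

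*Sharp cut (the extreme case).* If exactly the mildest fraction q is prevented, shift = 32 × φ(z_q)/(1 − q). For q = 0.20 this is 32 × 0.280/0.80 = 11.2 points. For q = 0.15 and 0.25 it is 8.8 and 13.6.

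*Graded prevention of 20% of colds.* The chance of prevention falls with severity on a logistic scale with slope b per SD, and the intercept is set so that 20% are prevented overall. The last column instead gives the remaining colds a true 16-point benefit.

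| b | Shift (points) | Chance of a significant 'worse' result | Power if the remaining colds are truly 16 points milder |
|---|---|---|---|
| 0 (unrelated to severity) | 0 | 2.5% | 77% |
| 0.5 | 3.1 | 7.6% | 59% |
| 1 | 5.6 | 16% | 44% |
| 2 | 8.4 | 33% | 28% |

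*Prevention of severe colds.* By symmetry of the normal distribution the sign reverses: preventing exactly the most severe 20% shifts the mean by 11.2 points in favour of vitamin D.

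*Sensitivity to shape.* With an exponential score of SD 32, the sharp 20% cut gives −32 × ln(0.80) = 7.1 points instead of 11.2.

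**4. What an all-randomized frequency comparison could detect.** As a rough guide, take a two-proportion test of any cold, 200 per arm, 32.4% on placebo. Power is 30%, 59% and 84% for relative reductions of 20%, 30% and 40%. For 80% power the vitamin D incidence must be 20.1% (relative risk 0.62).

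**The case against.** A reader might infer that the frequency half has no test at all. The document does not support that. III.D(11) and VI.D both commit to a between-arm comparison of frequency, and a statistical analysis plan that is not shown may name the model. What stands is narrower: VIII.B rewords a two-part hypothesis as one part and sizes it as though the other part had no effect.

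A reader might also infer that an effective vitamin D arm would look worse. That needs selective prevention of mild colds, and it needs the remaining colds not to become milder by enough to offset the shift. Nothing in the protocol says that mild colds are the ones prevented. If both halves of the hypothesis are true, the two influences oppose each other and the sign is undetermined.

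It is fair to add that a peak score exists only for someone with a cold, that the protocol is open about this population, and that whether colds are milder when they occur is a legitimate question. Using about 130 of 400 participants is therefore not a defect in itself, and the per-cold model need not be dropped. A score that sets people without a cold to 0 answers a different question. A total-burden score would be harder to justify here, because the protocol names only peak, day 1 and day 2 scores for analysis. None of this makes the conditional comparison a randomized one.

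**Conclusion.** The point holds in this limited form. VIII.B is inconsistent with III.B, III.D(11) and VI.D on what hypothesis 3 covers. Its only specified cold analysis conditions on a post-randomization event that treatment is hypothesised to change, and its power figures assume no effect on frequency.

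The resulting bias has no fixed direction. For 20% of colds prevented, it runs from 0 (prevention unrelated to severity), through about 3 to 8 points against vitamin D (graded preference for mild colds), to 11.2 points (exactly the mildest 20%), with the sign reversed if severe colds are prevented. Against the 16 to 18 points in the power table, the middle of that range is enough to matter. These figures rest on normal scores, SD 32 and no effect on the remaining colds; only the SD comes from the protocol.

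This concerns a secondary hypothesis. The primary analysis of time to treatment failure is not affected.

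**What to change.** In VIII.B, restate hypothesis 3 in both parts and add two analyses over all randomized participants:

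- (a) Number of colds per participant, by a negative binomial model with log follow-up time as offset, adjusted for the randomization strata (center partnership, BMI group, race).
- (b) Worst peak WURSS-21 score, with 0 for no cold, by a rank test stratified in the same way.

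Keep the per-cold repeated-measures model for peak, day 1 and day 2 scores. Label it as conditional on having had a cold, and interpret it together with (a) and (b). Add a sentence that the 65-per-group power assumes no effect on frequency.

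The cost is wording only, since cold counts and peak scores are already to be collected. The downside is that (b) mixes frequency with severity and is less sensitive to a pure severity effect. Power for frequency is also limited unless the reduction is large (step 4 of the working), and the text should say so.

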- 1 Research Network. Predicting worsening asthma control following the common cold. European
- 2 Resp J 2008;32:1-7.

XIII. APPENDICES

1

2

A. Appendix A. Exclusionary and Withhold Medications

Inhaled Steroids, except as provided in study Leukotriene modifiers (e.g., montelukast, zafirlukast, zileuton)	None None ≥ 6 weeks				
· · · · · · · · · · · · · · · · · · ·	≥ 6 weeks				
Oral Steroids, except as provided in study					
Cromolyn/Nedocromil	≥ 1 week				
Oral beta-adrenergic agonists	≥ 1 week				
Beta-adrenergic blockers	≥ 2 weeks				
Inhaled beta-adrenergic agonists (intermediate-acting, e.g., albuterol, terbutaline, metaproterenol, pirbuterol, bitolterol), except as provided in study	≥ 6 hours				
Long-acting Inhaled beta-adrenergic agonists (e.g., formoterol, salmeterol)	≥ 24 hours				
Short-acting anticholinergics (e.g., ipratropium)	≥ 6 hours				
Long-acting anticholinergics (e.g., tiotropium)	≥ 72 hours				
Short-acting theophylline (e.g., Slophyllin tablets)	≥ 12 hours				
Long-acting theophylline (e.g., Theo-Dur, Slo-BID)	≥ 24 hours				
Ultra long-acting theophylline (e.g., Theo-24, Uniphyl)	≥ 48 hours				
Macrolide antibiotics (chronic use)	≥ 4 weeks				
MAO inhibitors	≥ 4 weeks				
Colestipol	≥ 1 week				
Orlistat	≥ 1 week				
Cholestyramine	≥ 1 week				
Cardiac glycosides	≥ 1 week				
Phenytoin	≥ 1 week				
Phenobarbital	≥ 1 week				
Table 1. Drugs/Substances to be withheld throughout the study	Washout prior to Visit 0				
Vitamin D supplements (including cod liver oil) containing >1000 IU/day	≥ 6 weeks				
Calcium supplements > 2,500 mg/day	≥ 6 weeks				
Table 1. Drugs allowed during study, but must be withheld prior to skin testing	Washout prior to Visit 2 skin test				
Antihistamines (except for topical)	> 0 days				
 1st generation 2nd generation 	≥ 3 days ≥ 7 days				
 Zⁿ generation Nasal antihistamines 	≥ 7 days ≥ 5 days				

Table 1. Drugs allowed during study, but must be withheld prior to pulmonary function and/or methacholine challenge	Specified time period
Levalbuterol (study rescue drug)	≥ 6 hours
Oral decongestants (pseudoephedrine and others)	≥ 48 hours
Nasal decongestants (oxymetazoline and others)	≥ 6 hours
Oral antihistamines (chlorpheniramine and others)	≥ 48 hours
Nasal and ophthalmic antihistamines (azelastine nasal and others)	≥ 6 hours
Methylxanthine-containing foods or beverages (e.g., coffee, tea)	≥ 6 hours
Alcohol-containing foods or beverages	≥ 6 hours

1 2		B. Ap	opendix B. Modified Food Frequency Questionnaire (FFQ)
3 4	1)	•	u take vitamin D supplements or multivitamins that include vitamin D on a regular basis months)? Yes/No
5		a.	If yes, provide name
6		b.	If yes, number of capsules/tablets taken per day
7		c.	If yes, amount of vitamin D per capsule/tablet
8	2)	Do yo	u take cod liver oil on a regular basis (most months)? Yes/No
9		a.	If yes, how many teaspoons or capsules per day on average?
10	3)	How n	nany servings (8 oz glass) of milk do you consume on average?
11		a.	Number of servings per day
12		b.	Number of servings per week
13		C.	Does not regularly consume
14	4)	How n	nany servings of salmon (4 oz equivalent) do you consume on average?
15		a.	Number of servings per week
16		b.	Number of servings per month
17		c.	Does not regularly consume
18	5)	How n	nany servings of sardines (equivalent of a 3.7 oz can) do you consume on average?
19		a.	Number of servings per week
20		b.	Number of servings per month
21		c.	Does not regularly consume
22			
23			

1 2		C. Append	ix C. Sun Ex	posure Questic	onnaire (SEQ))								
3 4			•	estionnaire will be e participant sper		at visit 10 to ask specation.	ecifically about							
5	1.	In summer, during ye	our leisure time, how	w much time do you nor	mally spend in the sur	1								
6 7			< 1 hr a day	1 to 2 hrs per day	2 to 3 hrs per day	3 to 4 hrs per day	≥ 4 hrs a day							
8 9		The last 3 years	□ 1	□ 2	□з	 4	□ 5							
10 11	2.	In winter, during you	r leisure time, how of the control o	much time do you norma 1 to 2 hrs per day	ally spend in the sun 2 to 3hrs per day	3 to 4hrs per day	≥ 4 hrs a day							
12		The last 3 years	□1	\square_2	\square_3	\square_4	\square_5							
13														
14	3.	In summer, how much do your activities (playing, day sports, spectator sports, gardening, walking, etc.) take you outside												
15			Not that often	A moderate amount	Quite a lot	Virtually all the time								
16		The last 3 years	□ ₁	\square_2	\square_3	□ ₄								
17 18 19	4.	In winter, how much	do your activities (p	olaying, day sports, spec	etator sports, gardenin Quite a lot	g, walking, etc.) take you o	outside							
20		The last 3 years												
21 22	5.	·		you use a sunscreen or										
23			Never / rarely	Occasionally	Most of the time	Always / almost always								
24		The last 3 years	□1	\square_2	\square_3									
25	6.	In the last 3 years, h	ave you ever used	a sunlamp or a tanning l	oed at a tanning salon	? □₁Yes □₀No								
26		If Yes, how often?	□₁ At lea	ast once a week										
27			□₂ Less t	than once a week, but at	t least once a month									
28			□₃ Less t	than once a month, but r	more than two times a	year								
29			□₄ Less	than or equal to two time	es a year									
30														

D. Appendix D. Melanin Recording

SmartProbe 400 "L" measurements from four body areas. "L" is a measure of lightness or darkness (0=black, 100=white).

Body Area	First L Reading	Second L Reading				
Upper Inner Arm	0-100	0-100				
Outer Forearm	0-100	0-100				
Exposed Forehead	0-100	0-100				
Abdomen/Stomach	0-100	0-100				

E. Appendix E. Protocol Table.

Visit	0	1	2	3	4	5	6	7	8	9	10	TF***
Week	Pre- Scr	Scr	0	4	5	11	17	21	25	29	33	
Window (regular/extended)(Days)				+3/+7	-2/+7	±3/ ±5	±3/ ±5	±3/ ±5	±3/ ±5	±3/ ±5	±3/ ±5	
Randomization					Χ							
Steroid inhaler dose taper (if stable)							Χ		Χ			
Informed consent	Х											
Brief medical history	Χ											
Full medical history		Χ										
Long physical exam		Х									Χ	Χ
Short physical exam							Χ		Χ			
Height/weight/BMI		Х									Χ	
Body measurements (waist, hip, neck)		Х									Χ	
Melanin test				X							Χ	
Allergy skin testing ⁺⁺			Х									
Genetics blood sample				Х								
Serum vitamin D	Х						Х		Χ		Χ	
Serum calcium		Х										
Serum creatinine/eGFR		Х										
Urine calcium and creatinine ratio		Х		Х		Х	Χ		Χ		Χ	
Urine pregnancy test			X	Х			Х				Χ	
Spirometry		Х	X	Х	Х	Х	Х	Х	Χ	Х	Χ	Х
Maximum bronchodilator reversal		Х										
Methacholine challenge			X	X			Χ					
Sputum induction				Х			X ⁺					
Cold questionnaire (WURSS-21)					\ \ \ \ \ \ \ \ \ \ \ \ \ \ \ \ \ \ \							
distribution/instruction					X							
Asthma Control Test (ACT)		Х		Х		Х	Х	Х	Χ	Х	Χ	Х
Asthma Bother Profile (QOL) (ABP)		Х		X							Χ	
Asthma Symptom Utility Index (ASUI)		Х		X		Х	Χ	Χ	Χ	Χ	Χ	
Asthma-Specific Work Productivity and								İ				
Activities Impairment Questionnaire			X								Χ	
(WPAI:Asthma)												
Home Environment Questionnaire (HEQ)		Х										
Household Socio-Economic Information		Х										
questionnaire (HOUSEHOLD_SEI)		^										1
Perceived Stress Scale (PSS)			Х								Χ	

Visit	0	1	2	3	4	5	6	7	8	9	10	TF***
Week	Pre- Scr	Scr	0	4	5	11	17	21	25	29	33	
Window (regular/extended)(Days)				+3/+7	-2/+7	±3/ ±5	±3/ ±5	±3/ ±5	±3/ ±5	±3/ ±5	±3/ ±5	
Sinonasal Questionnaire (SNQ)				Х			Χ					
Sun Exposure Questionnaire (SEQ)				Х							Χ	
Vitamin D Intake Questionnaire				Х							Χ	
Review diaries				Х	Х	Х	Χ	Х	Χ	Х	Χ	Х
Review medication use				Х	Х	Х	Χ	Х	Χ	Х	Χ	
Satisfaction questionnaire											Χ	
Prednisone burst				Х								
Treatment failure assessment				Х	Х	Х	Χ	Х	Χ	Х	Χ	Х
Dispense e-diary/PEF meter			Х									
Dispense run-in medications (open-label ICS and single-blind vit D capsules)			Х	Х								
Dispense rescue prednisone supply					Х							
Dispense randomized medications (open-label ICS and double-blind vit D capsules)					Х	Х	Х	Х	Х	Х		

At visit 2, participants who did not show adequate bronchodilator reversal at visit 1 will complete spirometry, a urine pregnancy test (for women of child-bearing potential), and a methacholine challenge test.

^{**} The genetics blood sample may be postponed until the time of the vitamin D blood test at visit 6.

^{***} Additional visits to the clinical site will be required if the participant experiences treatment failure conditions between regular study visits.

⁺ Approximately 200 people will undergo sputum induction at visit 6. Only those whose sputum sample at visit 3 was deemed adequate through lab analysis will be eligible to have the sputum induction at visit 6.

⁺⁺ If washouts required for skin testing at visit 2 are not met, the skin test may be deferred to a future visit.
